9.1. Investigator Responsibilities

By signing this protocol, the Investigator agrees to conduct the study in an efficient and diligent manner and in conformance with this protocol; generally accepted standards of GCP; and all applicable local laws, rules and regulations relating to the conduct of the clinical study.

The Investigator also agrees to allow monitoring, audits, IRB review and regulatory agency inspection of trial-related documents and procedures and provide for direct access to all study related source data and documents.

The Investigator shall prepare and maintain complete and accurate study documentation in compliance with GCP standards and applicable local laws, rules and regulations; and, for each subject participating in the study, provide all data, and upon completion or termination of the clinical study submit any other reports to the Funder as required by this protocol or as otherwise required pursuant to any agreement with the Funder.

Study documentation will be promptly and fully disclosed to regulatory authorities by the Investigator upon request and also shall be made available at the Investigator's site upon request for inspection, copying, review and audit at reasonable times by representatives any regulatory agencies.

Persons debarred from conducting or working on clinical studies by any court or regulatory agency will not be allowed to conduct or work on this study.

9.2. Good Clinical Practice

The investigator will ensure that this study is conducted in accordance with the principles of the Declaration of Helsinki (as amended in Edinburgh, Tokyo, Venice, Hong Kong, and South Africa), International Conference on Harmonisation (ICH) guidelines. These standards are consistent with the European Union Clinical Trials Directive 2001/20/EC and Good Clinical Practice Directive 2005/28/EC. The investigator will ensure adherence to the basic principles of Good Clinical Practice, as outlined in 21CFR312, subpart D, "Responsibilities of Sponsors and Investigators," 21CFR, part 50, 1998, and 21CFR, part56, 1998. The investigator and all applicable sub investigators will comply with 21CFR, Part54, 1998, providing documentation of

their financial interest or arrangements with any study funder, or proprietary interests in the investigational drug under study. This documentation must be provided prior to the investigator's (and any sub investigator's) participation in the study. The investigator and sub investigator agree to notify study funder of any change in reportable interests during the study and for 1 year following completion of the study. Study completion is defined as the date when the last subject completes the protocol-defined activities

9.3. Institutional Review Board Review & Approval

The investigator will submit this protocol, informed consent form, and any accompanying material to be provided to the subject (such as advertisements, subject information sheets, or descriptions of the study used to obtain informed consent) to an IRB/IEC. The investigator will not begin any study subject activities until approval from the IRB/IEC has been documented and provided as a letter to the investigator. Before implementation, the investigator will submit to and receive documented approval from the IRB/IEC any modifications made to the protocol or any accompanying material to be provided to the subject after initial approval, with the exception of those necessary to reduce immediate risk to study subjects.

9.4. Informed Consent

The investigator is responsible for obtaining written informed consent from each individual participating in this study after adequate explanation of the aims, methods, objectives, and potential hazards of the study and before undertaking any study-related procedures. The investigator must use the most current IRB/IEC approved consent form for documenting written informed consent. Each informed consent will be appropriately signed and dated by the subject and the person conducting the consent discussion, and also by an impartial witness if required by local requirements.

9.5. Confidentiality

The investigator will assure that subjects' anonymity will be strictly maintained and that their identities are protected from unauthorized parties. Only subject initials, date of birth, another unique identifier (as allowed by local law) and an identification code will be recorded on any form or biological sample submitted to the study funder, IRB/IEC or laboratory. Laboratory

specimens will be labeled in such a way as to protect subject identity while allowing the results to be recorded to the proper subject. Refer to specific laboratory instructions for further details. NOTE: The investigator will keep a screening log showing codes, names, and addresses for all subjects screened and for all subjects enrolled in the trial. Subject data will be processed in accordance with all applicable regulations. The investigator agrees that all information received from the study funder, including but not limited to the Package Insert, the IMP, and any other study information, remain the sole and exclusive property of the study funder during the conduct of the study and thereafter. This information is not to be disclosed to any third party (except employees or agents directly involved in the conduct of the study or as required by law) without prior written consent from the study funder. The investigator further agrees to take all reasonable precautions to prevent the disclosure by any employee or agent of the study site to any third party or otherwise into the public domain.

9.6. Study Files and Retention of Records

The investigator will maintain adequate and accurate records to enable the conduct of the study to be fully documented and the study data to be subsequently verified. These documents should be classified into at least the following two categories: (1) investigator's study master file, and (2) subject clinical source documents. The investigator's study file will contain the protocol/amendments, CRF and query forms, IRB/IEC and governmental approval with correspondence, informed consent, drug records, staff curriculum vitae and authorization forms, and other appropriate documents and correspondence. The required source data should include sequential notes containing at least the following information for each subject:

- Subject identification (name, date of birth, gender);
- Documentation that subject meets eligibility criteria, i.e., history, physical examination, and confirmation of diagnosis (to support inclusion and exclusion criteria);
- Documentation of the reason(s) a consented subject is not enrolled
- Participation in study (including study number);

- Study discussed and date of informed consent;
- Dates of all visits;
- Documentation that protocol specific procedures were performed;
- Results of efficacy parameters, as required by the protocol;
- Start and end date (including dose regimen) of IMP, including dates of dispensing and return;
- Record of all adverse events and other safety parameters (start and end date, and including causality and severity);
- Concomitant medication (including start and end date, dose if relevant; dose changes);
- Date of study completion and reason for early discontinuation, if it occurs.

All clinical study documents must be retained by the investigator until at least 2years or according to local laws, whichever is longer, after the last approval of a marketing application in an ICH region (i.e., United States, Europe, or Japan) and until there are no pending or planned marketing applications in an ICH region; or, if no application is filed or if the application is not approved for such indication, until 2years after the investigation is discontinued and regulatory authorities have been notified. Investigators may be required to retain documents longer if specified by regulatory requirements, by local regulations, or by an agreement with study funder. The investigator must notify study funder before destroying any clinical study records. Should the investigator wish to assign the study records to another party or move them to another location, study funder must be notified in advance. If the investigator cannot provide for this archiving requirement at the study site for any or all of the documents, special arrangements must be made between the investigator and study funder to store these records securely away from the site so that they can be returned sealed to the investigator in case of an inspection. When source documents are required for the continued care of the subject, appropriate copies should be made for storage away from the site.

9.7. Electronic Case Report Forms

For each subject consented, an eCRF will be completed by an authorized study staff member whose training for this function is documented according to study procedures. The eCRF will be completed in a timely manner. Original entries as well as any changes to data fields will be stored in the audit trail of the system. At the conclusion of the trial, a read-only archive copy of the data entered will be generated. This archive will be stored in accordance with the records retention requirements.

9.8. Investigational Medicinal Product Accountability and Return

The investigator or designee is responsible for ensuring adequate accountability of all used and unused study drug. This includes acknowledgment of receipt of each shipment of study product (quantity and condition), subject dispensing records, and returned or destroyed study product. Dispensing records will document quantities received from study funder and quantities dispensed to subjects, including lot number, date dispensed, subject identifier number, subject initials, and the initials of the person dispensing the medication. Drug may be returned or destroyed on an ongoing basis during the study, if appropriate. At the end of the study, following final drug inventory reconciliation, the study site will arrange for the return of unused investigational medicinal product supplies. All drug supplies and associated documentation will be periodically reviewed and verified by the study funder over the course of the study.

9.9. Inspections

The investigator understands that source documents for this trial should be made available to appropriately qualified personnel from study funder and its representatives, to IRBs/IECs, or to regulatory authority or health authority inspectors.

9.10. Protocol Compliance

The investigator is responsible for ensuring the study is conducted in accordance with the procedures and evaluations described in this protocol.

9.11. Protocol Modifications

Protocol modifications, except those intended to reduce immediate risk to study subjects, may be made by the investigator in collaboration with the study funder. All protocol modifications must be submitted to the IRB/IEC in accordance with local requirements. Approval must be obtained before changes can be implemented.

9.12. Study Reports

A clinical study report (CSR) will be prepared and provided to the regulatory agency (ies). The Investigator will ensure that the report meets the standards set out in the ICH Guideline for Structure and Content of Clinical Study Reports (ICHE3). Note that an abbreviated report may be prepared in certain cases. After conclusion of the study, Investigators in this study may communicate, orally present, or publish in scientific journals or other scholarly media only after the following conditions have been met:

- The results of the study in their entirety have been publicly disclosed by or with the consent of the study funder in an abstract, manuscript, or presentation form.

9.13. Study Termination

The Investigator reserves the right to terminate the study at any time. Should this be necessary, the investigator will arrange discontinuation procedures and notify the appropriate regulatory authorities, IRBs, IECs, and the Funder. In terminating the study, the investigator will assure that adequate consideration is given to the protection of the subjects' interests.

10. References

1 INTRODUCTION

The purpose of this Statistical Analysis Plan (SAP) is to provide a description of the statistical methods to be implemented for the analysis of data from the study with protocol number NTZ-218-1. The SAP will be finalized prior to database lock. Any deviations from the SAP after database lock will be documented in the final Clinical Study Report (CSR).

2 STUDY OVERVIEW

2.1 Study Objectives and Endpoints

Primary	
Objective	Endpoint
To evaluate the safety and tolerability of NTZ 500 mg twice daily (BID) after 24 weeks of treatment in patients with non alcoholic steatohepatitis (NASH)-induced stage 2 or stage 3 fibrosis.	Adverse events (AEs) including treatment-emergent AEs (TEAEs) and serious AEs (SAEs), laboratory evaluations, vital signs, electrocardiograms (ECGs), and physical examinations.
Secondary	
Objective	Endpoint
To determine the effect of oral administration of NTZ 500 mg BID on de novo collagen synthesis through Fractional Synthesis Rate (FSR) of circulating plasma proteins in patients with NASH induced stage 2 or stage 3 fibrosis.	Percent change in FSR from baseline to end of treatment (24 weeks of treatment).
To assess changes in liver stiffness as measured by FibroScan® and by Magnetic Resonance Elastography (MRE).	Observed change in liver stiffness by FibroScan from baseline to 24 weeks of treatment Observed change in liver stiffness by MRE from baseline to 12 weeks and 24 weeks of treatment.
To assess the change from baseline in non-invasive markers of fibrosis: ELF™ test score, PIIINP, Hyaluronic acid, CK18, TIMP-1, YKL-40, Alpha 2 macroglobulin, miRNA, ProC3, ProC6, FGF19, and FGF21.	Observed change in non-invasive biomarkers of fibrosis from baseline to 12 weeks and 24 weeks of treatment.
To assess changes in additional non-invasive tests: fibrosis scores: non alcoholic fatty liver disease (NAFLD) fibrosis score and FIB-4.	Observed change in fibrosis scores from baseline to 12 weeks and 24 weeks of treatment.

2.2 Study Design

2.2.1 Overview

This is a Phase 2 proof of concept study to evaluate the safety and efficacy of open-label NTZ 500 mg BID in a NASH population with NASH induced Stage 2 or 3 fibrosis.

The study will include a screening visit within 6 weeks of randomization (i.e. Day 1) followed by a 24-week treatment period consisting of daily, BID, oral administration of NTZ and an end of treatment follow up period of 4 weeks.

Patients will come to the research center and complete the following visits:

- Screening Visit within 6 weeks of Randomization (i.e. Day 1)
- Day -14 Deuterated Water Run-In
 - Day-14, Day-11, Day-7 and Day 1: sampling for labeling of Deuterated water during run-in,
- Repeat baseline labs for alanine aminotransferase (ALT), aspartate aminotransferase (AST), total bilirubin, alkaline phosphatase, creatine kinase (CK) collected at least 4 weeks from initial screening.
- Day 1 randomization: start of treatment
- Every 4 weeks after randomization until 20 weeks post randomization
- 22 weeks post enrollment and Deuterated Water Administration Period
 - 22 weeks plus 3 days
 - Sampling for labeling of Deuterated Water on Day 155, Day 158, Day 162, and Day 169
- 24 weeks post randomization: End of Treatment
- Week Post Treatment Follow Up

2.2.2 Randomization and Blinding

There is only one treatment group; there is no randomization. Any use of “randomization” refers to enrollment Day 1 (i.e. subject passed screening and will enter the treatment period). This is an open-label study; there is no blinding.

2.2.3 Study Drug

Patients will receive 500 mg NTZ (ALINIA®) twice daily for 24 weeks. NTZ will be supplied as 500 mg of ALINIA (nitazoxanide) tablets, for oral use. The tables are round, yellow, film-coated and debossed with ALINIA on one side and 500 on the other side. Each tablet contains 500 mg of nitazoxanide.

2.2.4 Sample Size Determination

The sample size of this Phase 2 proof of concept study is based on clinical assessment. Twenty male and female subjects with histologically confirmed NASH and fibrosis stage 2 or 3 will

provide sufficient information to assess the safety and tolerability of NTZ 500mg BID over 24 weeks.

3 STATISTICAL METHODOLOGY

3.1 General Considerations

3.1.1 Analysis Day

Analysis day will be calculated from the date of first dose of study drug. The day of the first dose of study drug will be Day 1, and the day immediately before Day 1 will be Day -1. There will be no Day 0.

3.1.2 Analysis Visits

Scheduled visits will be assigned to analysis visits as recorded on the case report form (CRF). Where applicable, early termination visits will be summarized with Visit 10 Week 24 (i.e. Visit 10 Week 24/Early Termination).

3.1.3 Definition of Baseline

For FibroScan and MRE, baseline is defined as the last measurement on or prior to the day of the first dose of study drug. In other words, time is not taken into consideration.

Otherwise, baseline is defined as the last measurement prior to the first dose of study drug (generally should be the Day 1 pre-dose assessment). In other words, time is taken into consideration.

3.1.4 Summary Statistics

Categorical data will generally be summarized with counts and percentages of subjects. The denominator used for the percentage calculation will be clearly defined in the table. Continuous data will generally be summarized with descriptive statistics including n (number of non-missing values), mean, standard deviation, first quartile (Q1), median, third quartile (Q3), minimum, and maximum.

3.1.5 Hypothesis Testing

This is a proof of concept study to assess the safety and tolerability of NTZ 500 mg BID over 24 weeks. There will be no formal hypothesis testing.

3.1.6 Handling of Dropouts and Missing Data

All data will be analyzed as observed. Dropouts and missing data will not be imputed.

3.2 Analysis Populations

3.2.1 Full Analysis Set

The Full Analysis Set consists of all subjects that meet the eligibility criteria and enroll into the study (Visit 1 Day 1).

The Full Analysis Set will be the primary population for all efficacy analyses. Only subjects with results for the specified efficacy parameter will be included in each analysis.

3.2.2 *Safety Analysis Set*

The Safety Analysis Set consists of all enrolled subjects who receive at least one dose of study drug.

The Safety Analysis Set will be the primary population for all safety analyses.

3.3 Subject Data and Study Conduct

3.3.1 *Subject Disposition and Analysis Populations*

Counts and percentages of subjects who were screened (signed informed consent), discontinued early during screening (screen failures), and enrolled (Full Analysis Set) will be summarized in total based on all screened subjects. Reasons for early discontinuation will also be summarized.

Counts and percentages of subjects in the Full Analysis Set, Safety Analysis Set, discontinued early from the study, and completed the study will be summarized based on the Full Analysis Set. Reasons for early discontinuation will also be summarized.

3.3.2 *Protocol Deviations*

Protocol deviations will be logged in the Medpace ClinTrak system. All protocol deviations will be listed.

3.3.3 *Demographic and Baseline Characteristics*

The following demographic and baseline characteristics will be summarized based on the Full Analysis Set:

- Age (years) at informed consent and age categories (<65 years, ≥65 years),
- Sex,
- Race,
- Ethnicity,
- Height (cm) at Screening,
- Baseline weight (kg), and
- Baseline body mass index (BMI) (kg/m²).

3.3.4 *Medical History*

All medical history will be listed.

3.3.5 *Concomitant Medications*

Prior and concomitant medications will be coded to anatomical therapeutic chemical (ATC) class and preferred term using the World Health Organization (WHO) Drug Dictionary version Global B3 September 2018. For summary purposes, medications will be considered prior medications if they stopped prior to the first dose of study drug and concomitant medications if they were taken at any time after the first dose of study drug (i.e. started prior to the first dose of study drug and were ongoing at the time of the first dose of study drug, or started after the first dose of study drug). Medications cannot be counted as both prior and concomitant.

If a medication has incomplete start or stop dates, dates will not be imputed to determine whether a medication should be considered prior or concomitant. If the date is missing but it is

known that the medication was taken within the same month as the first dose of study drug, it will be considered concomitant. If the date and month are missing but it is known that the medication was taken within the same year as the first dose of study drug, it will be considered concomitant.

Counts and percentages of subjects taking prior and concomitant medications by ATC class and preferred term will be summarized based on the Safety Analysis Set.

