6.5.2. Early Termination (ET)

Patients who have discontinued from the study after the first dose of study medication and for any reason will have the following procedures completed:

- Complete physical examination
- Record vital signs
- Weight, BMI
- ECG
- Record concomitant medication taken
- MRE (may be done within ± 5 days of the visit)

- Fibroscan
- Adverse Events assessment
- Blood samples will be collected
- Urine samples will be collected for Urinalysis
- Urinary pregnancy test (for women of childbearing potential only [WOCBP])
- Review study drug compliance with subject
- Reconcile study drug administration using pill counts
- Documentation if Early Termination is due to COVID-19 related AE or concerns.

6.5.3. **Unscheduled Visits**

An unscheduled visit is defined as any visit to the study unit outside of the protocol-evaluation time points where the patient is seen by study unit personnel, e.g., when follow-up assessments are required for safety reasons or when repeat measurements are required out of the screening period (either to confirm a measurement or in case of errors, measuring device failure, etc.).

Unscheduled visits will be needed for patients who may require further follow-up due to safety.

6.6. **Missed or Partially Completed Visits due to COVID-19**

If a subject is unwilling or unable to complete regularly scheduled visit(s) due to COVID-19, the study team will document the following:

- Was the visit partially completed (some procedures completed, while other protocol directed procedures were not completed)? If so:
 - Clinical safety lab tests (hematology, coagulation, pregnancy test, and biochemistry), as required by the visit schedule, must be completed to dispense NTZ to the patient for continued safety monitoring.
- Was any part of the visit performed via a virtual method (e.g. phone, or other technology)? These procedures must be clearly documented as being done “virtually” in the source documentation.
- Description why the visit was partially completed or missed.
- Any COVID-19 related symptoms defined below since the last visit, to include AE onset date, description and resolution date:
 - Fever
 - Cough

- Shortness of breath
- Other symptom as defined by the Centers for Disease Control and Prevention.

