6.7. Assessment for Premature Discontinuation from Study

Study medication may be discontinued in the following instances:

- Intercurrent illness that would, in the judgment of the investigator, affect assessments of clinical status to a significant degree. Following resolution of intercurrent illness, the subject may resume study dosing at the discretion of the investigator.
- Subject noncompliance
- Investigator discretion
- Study medication must be discontinued in the following instances:
 - Unacceptable toxicity, or toxicity that, in the judgment of the investigator, compromises the ability to continue study-specific procedures or is considered to not be in the subject's best interest
 - Subject request to discontinue for any reason
 - Pregnancy
 - Discontinuation of the study at the request of a regulatory agency or an institutional review board or independent ethics committee (IRB/IEC)

Pre-specified stopping criteria are defined at the patient level and at the study level. These are described in the following sections 6.6.1., 6.6.2., and 6.6.3. In all cases, when the stopping criteria are met, the Data Safety Monitoring Board will perform causality assessment, and decide whether the study drug/study trial may be continued (See section 6.6.4.).

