6.6.3. Dose Adjustment

Enrolled subjects who experience treatment emergent adverse events should be monitored closely and may have the NTZ dose adjusted at the Principal Investigator's discretion.

Enrolled subjects who experience a possible treatment emergent adverse event will be assessed for symptoms and further biochemical assessments as follows:

- GI Adverse Events: the subject will be assessed for abdominal pain, loss of appetite, nausea and vomiting. Blood will be collected for amylase and lipase assessment to rule out pancreatitis.
- Kidney Function Adverse Events: the subject will have blood samples collected for eGFR to rule out kidney dysfunction.
- Musculoskeletal Adverse Events: the subject will be assessed for fatigue, muscle aches and pain. Blood samples will be collected for Creatine Kinase.

The following procedure will be followed for dose adjustments:

1. Patients will be asked to hold drug for 3 days
2. After the 3-day drug hold, patients will be reassessed for adverse event symptoms.
 - If the AE symptoms have resolved following 3 days of drug hold, the patient will discontinue NTZ dosing permanently and will be followed per the schedule of assessments.

If the AE symptoms have not resolved following 3 days of drug hold, the patient will be restarted on a reduced dose of 500 mg NTZ, once a day for 7 days. Patients will be evaluated for treatment emergent adverse events and consideration for resuming the dosage of 500mg NTZ twice a day. PI may determine that the patient should remain at the 500 mg NTZ once a day dose following 7 days of reduced dose. In such scenarios, the patient will be monitored and consideration for resuming the dosage of 500 mg NTZ twice daily will be evaluated at each subsequent visit.

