3.5 Safety Assessments

3.5.1 Adverse Events

All AEs regardless of seriousness or relationship to study drug, including those occurring during the Screening Period, are to be recorded on the corresponding page(s) of the CRF and in the patient's medical record from the informed consent form signature until study end for each patient. All AEs will be coded to system organ class and preferred term using Medical Dictionary for Regulatory Activities (MedDRA) version 21.0.

TEAEs are defined as AEs that worsen in severity or relationship to study drug or commence on or after the time of start of first study drug administration. This may include AEs that start during follow-up after the last dose of study drug.

Study drug related AEs are defined as AEs that are possibly related or related.

An overview of AEs based on the Safety Analysis Set will be provided including counts and percentages of subjects with the following:

- Any TEAEs (overall and by maximum severity)
- Any study drug related TEAEs (overall and by maximum severity)
- Any SAEs
- Any study drug related SAEs
- Any deaths due to AEs
- Any AEs leading to withdrawal from study or study drug
- Any study drug related AEs leading to withdrawal from study or study drug

Counts and percentages of subjects will also be presented by system organ class and preferred term for TEAEs and study drug related TEAEs. In addition, summaries will be provided by system organ class, preferred term, and maximum severity.

Listings will be presented specifically for SAEs and TEAEs leading to withdrawal from study or study drug.

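### The SAP has no study-drug disposition: it does not define study completion, and no planned table cleanly shows how many patients completed 24 weeks of NTZ or why the others stopped

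*SAP*

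**What the plan says.** **Disposition.** Under SAP 3.3.1, after the screening counts, the subjects in each analysis set and those who "discontinued early from the study, and completed the study will be summarized based on the Full Analysis Set". It adds that "Reasons for early discontinuation will also be summarized". That sentence follows the study-level categories, so on plain reading the reasons are for leaving the study. No category refers to study drug, and study completion is not defined.

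**Stopping drug while staying in the study.** In the dose-adjustment procedure of protocol 6.6.3, one branch reads: "the patient will discontinue NTZ dosing permanently and will be followed per the schedule of assessments". I cite it only to show that follow-up off drug is foreseen, not to comment on the rule.

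**Leaving the study.** Protocol 6.5.2 reserves the Early Termination visit for "Patients who have discontinued from the study after the first dose of study medication and for any reason". Leaving the study is the trigger, not stopping the drug.

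**Reasons for stopping drug.** The title of protocol 6.7 concerns discontinuation from the study, but its text opens with "Study medication may be discontinued in the following instances". It lists intercurrent illness, noncompliance and investigator discretion. Among the mandatory reasons it includes "Subject request to discontinue for any reason".

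**AE tables.** The SAP 3.5.1 overview has rows for "Any AEs leading to withdrawal from study or study drug" and "Any study drug related AEs leading to withdrawal from study or study drug", plus a listing of TEAEs pooled in the same way. Protocol 8.5.1 plans numbers and percentages of subjects with TEAEs leading to study drug discontinuation, by system organ class and preferred term. SAP section 6 declares no changes from the protocol's analysis.

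**Exposure and compliance.** SAP 3.3.6 summarizes days from first to last dose in seven bands. The last two are 141 to 168 days, and 169 days or more (labelled as at least 24 weeks). Expected doses for compliance are twice the days of exposure.

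**The concern.** The primary objective is safety and tolerability of NTZ 500 mg BID over 24 weeks. In a single-arm study of 20 patients, a direct measure of tolerability is how many took the drug to the end, and why the rest did not. Stopping the drug and leaving the study are different events in this protocol, but the disposition table describes only the second. If some patients stop NTZ and keep attending, the completion rate in that table will be higher than the treatment completion rate, and nothing beside it will say so. A reader of the study report may then take study completion as evidence of tolerability.

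**Working it through.** The plan states no figure to reproduce on this point. The check follows one type of patient through each planned table, with the small arithmetic that this needs.

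**1. Disposition (SAP 3.3.1).** Take a patient who stops NTZ for good in Week 5 under protocol 6.6.3 and attends to Week 28. The Early Termination visit is not triggered, because the patient has not left the study. The patient reaches the end-of-study visit and, on plain reading, is a completer. This is an inference, because completion is undefined and protocol 6.7 mixes drug and study discontinuation.

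**2. AE overview (SAP 3.5.1).** If an AE caused the stop, the patient is counted in the withdrawal row and appears in the listing. The row also contains patients who left the study, so the number who stopped NTZ because of an AE cannot be read from it. The by-class, by-term summary in protocol 8.5.1 would isolate drug discontinuation, but SAP 3.5.1 does not include it and SAP section 6 does not record the omission.

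**3. Non-AE reasons (protocol 6.7).** If the patient stopped by request, for noncompliance or at the investigator's discretion, and stayed in follow-up, the AE rows do not apply. The reasons in SAP 3.3.1 apply to leaving the study. No summary table remains.

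**4. Exposure bands (SAP 3.3.6).** Days of exposure = last dose date − first dose date + 1.
- Twenty-four weeks: 24 × 7 = 168 days.
- First dose on Day 1, last dose on Day 168: 168 − 1 + 1 = 168 days, which falls in the 20 to <24 weeks band.
- Last dose on Day 141: 141 days, the same band, although this is 168 − 141 = 27 days short of 24 weeks.
- Reaching the top band takes a dose on Day 169. Protocol 6.4.6 (Week 24, Day 169) lists no dose administration, whereas the Week 4 to Week 20 visits do.

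Anyone stopping before Day 141 is visible as an early stopper. In the 141 to 168 band, full-course patients and early stoppers can be mixed.

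**5. Compliance (SAP 3.3.6).** A patient who takes every dose through Day 35 has 2 × 35 = 70 expected and 70 taken: 100 × 70/70 = 100%. The denominator ends at the last dose, so early stopping does not lower this figure.

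**6. Size.** One patient is 1/20 = 5 percentage points. With no study withdrawals and *k* patients who stop NTZ but keep attending:

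| *k* (assumed) | Study completers | Treatment completers | Difference |
|---|---|---|---|
| 0 | 20/20 (100%) | 20/20 (100%) | 0 points |
| 1 | 20/20 (100%) | 19/20 (95%) | 5 points |
| 2 | 20/20 (100%) | 18/20 (90%) | 10 points |
| 4 | 20/20 (100%) | 16/20 (80%) | 20 points |

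The documents give no discontinuation rate, so every row is illustrative.

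**The case against.** A reader might infer that NTZ discontinuation and its reasons are never tabulated. The documents do not support that. SAP 3.5.1 gives counts and percentages for AE-driven and drug-related AE-driven withdrawals, including withdrawal from study drug, and lists the events. The 6.6.3 route is itself triggered by adverse events, so a patient who stops by that route should appear there. Nor does the disposition table report completion alone: it also gives early study discontinuation with reasons.

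A reader might also infer that early stoppers would be hidden. They would not be. The exposure table, on the Safety Analysis Set, shows most of them in its shorter bands. SAP section 7 puts all available data in subject listings, and with 20 patients at one site these can be read case by case. Detailed programming specifications are in a separate document, which may add tables.

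The non-AE gap is also conditional. Protocol 6.7 does not say that patients who stop for those reasons stay in the schedule. If they leave the study, SAP 3.3.1 gives their reason. Finally, a study-completion rate does not claim to be a treatment-completion rate.

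All of this stands, and it limits the point to a reporting gap. It does not close the gap. Pooled rows cannot be separated, duration carries no reason, the top exposure band misses a patient with exactly 168 days, and listings do not replace a summary for the primary objective.

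**Conclusion.** The point holds as a reporting weakness. SAP 3.3.1 lacks study-drug disposition and a definition of study completion. AE-driven NTZ withdrawal is counted only together with study withdrawal. Non-AE reasons for stopping NTZ while staying in the study have no summary table. The exposure bands do not cleanly separate patients who completed 24 weeks of NTZ from those who stopped in the last four weeks.

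The size is 5 percentage points per patient off drug but still attending, out of 20. How many there would be is an assumption, and 16/20 is not a forecast. Counting such patients as completers is the plain reading, not a stated rule. The non-AE part assumes that some of these patients stay in follow-up, which the protocol neither states nor rules out. No endpoint, test, analysis set or sample size is affected. The change is still worth making because it bears on the primary objective and costs little.

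**What to change.** In SAP 3.3.1:
- Define study completion.
- Add treatment disposition on the Safety Analysis Set beside study disposition: completed 24 weeks of NTZ, or permanently discontinued NTZ, with primary reason and day of last dose.
- Define treatment completion explicitly, so that it does not depend on the 169-day band in SAP 3.3.6.

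In SAP 3.5.1:
- Report AEs leading to study drug discontinuation separately from AEs leading to study withdrawal, both overall and for drug-related events.
- Restore the protocol 8.5.1 summary, by system organ class and preferred term, of TEAEs leading to study drug discontinuation, or record its omission in SAP section 6.

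The cost is SAP wording, one extra disposition table, and the AE summary if it is restored. The inputs are already required: action taken with the drug for each AE (protocol 7.2.3), duration and reason of any interruption (protocol 5.5), drug end date and reason for early discontinuation (protocol 9.6), and last dose date on the end of study form (SAP 3.3.6). Before finalizing, check that the case report form holds the reason for stopping NTZ separately from the reason for leaving the study. The sample size and visit schedule do not change.
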